7.2. Rationale and Discussion of Study Design

The first part of this study is a randomized, double-blind, placebo-controlled study of the safety, tolerability, PK, and efficacy study of trifarotene cream HE1 100 µg/g and 200 µg/g in subjects with LI.

In a previous proof-of-concept study (RD.03.SRE.40181E), subjects with LI applied trifarotene 50 and 100 µg/g cream to limited areas and results demonstrated a decrease in scaling with good safety and tolerance. In a phase 1 study in healthy Japanese and non-Japanese subjects (RD.03.SPR.103813), repeated topical applications of trifarotene (CD5789 cream HE1) 100 µg/g and 200 µg/g resulted in low and similar CD5789 systemic levels in all the cohorts. These studies are fully described in the current IB.

To ensure safety, this phase 2 study will begin with an initial cohort (Cohort A) of 15 subjects randomized 1:1:1 to trifarotene cream HE1 100 µg/g, 200 µg/g, or vehicle to be applied twice weekly. An independent DSMB will review aggregate safety and tolerability data from the initial 15 subjects' first 28 days of treatment. If no safety issues are identified, 105 additional subjects will be allowed to enroll in Cohort B and randomized to trifarotene cream HE1 100 µg/g, trifarotene cream HE1 200 µg/g, or vehicle and treated twice weekly in the same manner as subjects in Cohort A. All subjects in the randomized, double-blind portion of the study will be treated for up to 12 weeks and data on safety, tolerability, PK, and efficacy collected.

Subjects who successfully complete the initial 12 weeks of double-blind treatment will have the option to enter an OLE with trifarotene cream HE1 200 µg/g twice weekly for up to 12 weeks.

The OLE will collect additional safety, tolerability, PK, and efficacy data. As designed, this study will provide important information on safety, tolerability, and PK with dosing of subjects with LI for up to 6 months.

The protocol includes appropriate monitoring for safety and tolerability. If subjects develop significant local application site reactions or tolerability issues, the protocol includes language for reducing the frequency of application or halting study drug application until the symptoms abate.

7.3. Selection of Doses in the Study

Based on the results from Study RD.03.SRE.40181E and Study SRE.103813, the doses of 100 µg/g and 200 µg/g were selected for further investigation in subjects with moderate to severe LI to determine which of the 2 doses is most effective. The PoC study demonstrated efficacious treatment with 100 µg/g in adults. The PK and tolerability study showed that, when the frequency of application was reduced from daily to twice weekly, the 200 µg/g cream HE1 had good local tolerability.

Therefore, the current study will use these doses compared with vehicle, applied twice weekly on up to approximately 90% BSA in subjects with LI. The OLE will evaluate the long-term safety of the higher dose in this patient population.

7.4. Study Sites

The study will take place at approximately 40 sites in North America, Europe, Israel, and Australia.

7.5. Point of Contact

A point of contact will be identified to provide information to subjects about where to obtain information on the study, the rights of subjects, and whom to contact in case of a study-related injury. This information will be provided in the subject information and informed consent form (ICF).

7.6. End of Study Definition

A clinical trial is considered completed when the last participant's last study visit has occurred.

8. SUBJECT POPULATION

8.1. Selection of Study Population and Diagnosis

Diagnosis of LI for the purposes of this study will be a clinical diagnosis. Although some younger subjects may have had genetic testing, older subjects may not.

While LI is a rare disease and subject enrollment may be challenging, due to possible bias introduced by including household members in the same study, it is recommended that only 1 household member be included in the study to maintain the blind and ensure all assessments are independent.

8.2. Study Entry Criteria

8.2.1 Inclusion Criteria

A subject will be eligible for study participation if he or she meets all of the following criteria:

1. Subject is ≥ 18 years old.
2. Subject has known diagnosis of LI.
3. Subject has moderate to severe (IGA 3–4) LI on the IGA of LI severity.
4. Subject has signed an ICF at Screening before any investigational procedures.
5. Subject who is participating in optional photography has signed a photography ICF.
6. Subject who is participating in the optional PK substudy has signed a PK ICF.
7. Subject is not of childbearing potential, i.e., a female who is postmenopausal (absence of menstrual bleeding for 1 year before Baseline, without any other medical reason, hysterectomy or bilateral oophorectomy),

OR

- Subject is a woman of childbearing potential (WOCBP) or a male subject with sexual partners capable of reproduction who agrees to use 2 effective forms of contraception during the study and for at least 1 month after the last study drug application. The 2 authorized forms of contraception are condom used with 1 of the following methods of contraception:
 - bilateral tubal ligation
 - combined oral contraceptives (estrogens and progesterone) or implanted or injectable contraceptives with a stable dose for at least 1 month before Baseline; hormonal contraceptives must inhibit ovulation
 - hormonal intrauterine device (IUD) inserted at least 1 month before Baseline

OR

Agrees to abstain from heterosexual intercourse during study participation and for 1 month after the last application of study drug and to use a highly effective contraceptive as backup if he or she becomes sexually active during the study. Abstinence is only acceptable if this is the subject's usual lifestyle. Periodic abstinence (calendar, symptothermal, postovulation methods), withdrawal (coitus interruptus), spermicides only, and lactational amenorrhoea method are not acceptable methods of contraception.

AND

Male subjects may not donate sperm during the study and for at least 1 month after the last study drug application.

8. Women of childbearing potential must be nonlactating and have negative pregnancy test results at Screening (serum) and on Day 1 before study drug administration (urine).
9. Subject is reliable and capable of adhering to the protocol and visit schedule, in the investigator's judgment, and has signed informed consent.
10. Subject is taking no more than 3500 IU/day Vitamin A (e.g., as in a multivitamin).

8.2.2 Exclusion Criteria

A subject will be excluded from the study if he or she meets any of the following criteria:

1. Subject has any variant of ichthyosis other than LI or another disorder of keratinization, including syndromic ichthyoses.
2. Subject has current moderate or severe stinging/burning at Screening.
3. Subject has an ongoing cutaneous infection or any other significant concomitant skin disease (other than the LI) which, in the investigator's opinion, may interfere with the study assessments.
4. Subject with a known lipid disorder (hypertriglyceridemia >200 mg/dL, hypercholesterolemia >250 mg/dL) unless well controlled by stable doses of lipid-lowering agents for at least 6 months.
5. Subject was previously treated with trifarotene/CD5789 in an acne or ichthyosis study.
6. Subject has any other significant concomitant disease, or poorly controlled medical condition other than LI that in the investigator's opinion may put him or her at risk if he or she takes part in the study, and/or that may interfere with the study assessments.
7. Subject has a medical condition that potentially alters bone metabolism (e.g., osteoporosis, thyroid dysfunction, Cushing syndrome, Crohn's disease, or ulcerative colitis).
8. Subject is being treated for major depression disorder and/or has a history of major depression or suicide attempt requiring hospitalization, medications, and close psychiatric surveillance to prevent suicide attempts.
9. Subject with positive serology for hepatitis B surface antigen, hepatitis C, or are known to be HIV positive or to have AIDS at Screening.
10. Subject with any of the following laboratory values at Screening:
 - a. Aspartate aminotransferase or alanine aminotransferase $>1.5 \times$ upper limit of normal defined by the laboratory
 - b. Total bilirubin >1.1 mg/dL or, in case of Gilbert's syndrome, total bilirubin >3 mg/dL
 - c. Hemoglobin <12.5 g/dL for men and <11.5 g/dL for women
 - d. Platelets $<150 \times 10^9/L$ or $>400 \times 10^9/L$.
11. Subject has any clinically other significant abnormal laboratory value (hematology, chemistry, or urinalysis) at Screening that, in the investigator's opinion, may put the subject at risk if he or she takes part in the study, and/or that may interfere with the study assessments.
12. Subject has had recent systemic malignancy (e.g., within 5 years) with exception of nonmelanoma skin cancer or cervical intraepithelial neoplasia of Grade 1 who are >6 months post-treatment.

13. Subject has a history of long QT syndrome or clinically significant ECG abnormalities, including clinically significant conduction disorders or significant arrhythmias, QTcF interval >450 ms, PR interval is not between 120 and 220 ms (inclusive), HR >100 bpm or <50 bpm, QRS interval >110 ms, or QT intervals that cannot be consistently analyzed.
14. Subject has a known allergy or sensitivity to any of the components of the investigational products.
15. Subject has been exposed to excessive UV radiations on the treated zones within 1 month before Baseline visit or is planning intensive UV exposure during the study (e.g., occupational exposure to the sun, sunbathing, phototherapy, etc.).
16. Subject is inherently sensitive to sunlight.
17. Subject is unable or unwilling to stop use of topical or systemic retinoids.
18. Subject is presumed to be abusing drug or alcohol at Screening or Baseline Visits based on medical history or current clinical symptoms.
19. Subject is participating in another interventional clinical trial.
20. Subject is institutionalized.
21. Subject is in any way related to the sponsor, investigator, or site personnel.

8.3. Premature Subject Withdrawal

All subjects will be advised that they are free to withdraw from participation in this study at any time, for any reason, and without prejudice. The investigator should make every reasonable attempt to keep subjects in the study; however, subjects must be withdrawn from the study if they withdraw consent to participate. Investigators must attempt to contact subjects who fail to attend scheduled visits by telephone or other means to exclude the possibility of an AE being the cause of withdrawal. Should this be the cause, the AE must be documented, reported, and followed as described in Section 11.2.

The sponsor reserves the right to request the withdrawal of a subject due to protocol deviations or other reasons.

The investigator also has the right to withdraw subjects from the study at any time for lack of therapeutic effect that is intolerable or otherwise unacceptable to the subject, for intolerable or unacceptable AEs, intercurrent illness, noncompliance with study procedures, administrative reasons, or in the investigator's opinion, to protect the subject's best interest.

If a subject is withdrawn before completing the study, the reason for withdrawal and the date of discontinuation will be recorded on the appropriate page of the electronic case report form (eCRF). Whenever possible and reasonable, the evaluations that were to be conducted at the completion of the study should be performed at the time of premature discontinuation.

8.4. Discontinuation of Study Intervention

Discontinuation from study treatment does not mean withdrawal from the study, and the remaining study procedures should be completed as indicated in the study protocol (see Section 10.2.4.5). If a clinically significant finding is identified (including, but not limited to changes from Baseline) after enrollment, the investigator or qualified designee will determine if any change in participant management is needed. Any new clinically relevant finding will be reported as an AE.

An investigator must discontinue a participant's study treatment for any of the following reasons:

- Pregnancy
- Significant study intervention noncompliance
- If any clinical AE, laboratory abnormality, or other medical condition or situation occurs such that continued participation in the study would result in a significant burden to the participant
- If the participant meets an exclusion criterion (either newly developed or not previously recognized) that precludes further study participation

The reason for discontinuation of study treatment will be recorded on the eCRF. Subjects who sign the informed consent form and are randomized but do not receive the study intervention may be replaced. Subjects who sign the informed consent form, are randomized, and receive the study intervention, and subsequently discontinue study treatment, or are withdrawn from the study will not be replaced.

A participant will be considered lost to follow-up if he or she fails to return for 3 scheduled visits and is unable to be contacted by the study site staff.

The following actions must be taken if a participant fails to return to the clinic for a required study visit:

- The site will attempt to contact the participant and reschedule the missed visit and counsel the participant on the importance of maintaining the assigned visit schedule and ascertain if the participant wishes to and/or should continue in the study.
- Before a participant is deemed lost to follow-up, the investigator or designee will make every effort to regain contact with the participant (where possible, 3 telephone calls and, if necessary, a certified letter to the participant's last known mailing address or local equivalent methods). These contact attempts should be documented in the participant's medical record or study file.
- Should the participant continue to be unreachable, he or she will be considered to have withdrawn from the study with a primary reason of lost to follow-up.

8.5. Subject Replacement Criteria

Withdrawn subjects will not be replaced. If a substantial number of subjects are withdrawn from the study, the sponsor will evaluate the need for developing replacement criteria.

Randomized subjects withdrawn from the study may not reenter. The subject number for a withdrawn subject will not be reassigned to another subject.

9. TREATMENTS

9.1. Identification of Investigational Product(s)

Trifarotene cream HE1 is a cream containing 100 or 200 µg/g (0.01% [w/w] or 0.02% [w/w], respectively) of CD5789 and the following excipients: purified water, propylene glycol, allantoin, glycerin, medium-chain triglycerides, polypropylene glycol 15 stearyl ether, cyclomethicone, phenoxyethanol, copolymer of acrylamide and sodium acryloyldimethyltaurate, dispersion 40% in isohexadecane (simulgel 600 PHA), sodium benzoate, butylated hydroxytoluene, and gluconolactone. It is an RAR γ agonist characterized by its high specificity to this receptor.

Vehicle contains the same ingredients, without the CD5789.

Trifarotene cream HE1 and vehicle will be provided in cream form for topical application and will be supplied in 50-g tubes from which a maximum of 36 g of IP may be extracted.

Trifarotene cream HE1 and vehicle will be supplied by G. Production, Inc. (Galderma) in Baie-D'Urfé, QC, Canada.

9.2. Treatments Administered

For the Double-blind Treatment Period, a fixed dose (determined at Visit 2) of trifarotene cream HE1 100 µg/g or 200 µg/g or vehicle cream will be applied topically twice weekly on up to 90% BSA of each subject. The IP should be applied thinly and gently rubbed in.

Study staff will apply the first administration of IP in the clinic on Day 1 after Baseline measurements, and the amount of IP used will be measured (i.e., 50-g tube will be measured before and after application to determine amount used). If the product will be applied at home by someone other than the study subject, it is recommended that this person assist with application at the first visit to learn how the IP is applied.

The maximum dose per application is 36 g (i.e., 1 tube). Subjects will receive an adequate number of tubes to use 1 tube per application and will use a new tube for each treatment day. Subjects may use less than full amount of product in a tube. Subjects will continue treatment for up to 12 weeks.

After the Day 1 visit, subjects will apply approximately the same amount (up to 36 g) of study drug as for the first dose on up to 90% of BSA twice weekly, sparing the scalp, inguinal, and axillary areas. Subjects with heavy facial hair should not apply IP to hair-bearing areas. Persons other than the study subject applying the study drug must wash their hands after application or use disposable vinyl gloves. In addition, a long-handled applicator will be provided for application on the back. The applicator must be washed with warm water and soap after every application.

Trifarotene cream should not come into contact with the eyes, mouth, angles of the nose, or mucous membranes. For the ectropion treatment, Q-tips are recommended for precise application on eyelids, without contact to the eye or conjunctiva. If the IP gets into the eye, it must be flushed immediately with warm water. In case of eye irritation, the subject must be seen by an ophthalmologist.

For the OLE, all subjects will receive trifarotene cream HE1 200 µg/g and apply the same fixed dose in the same manner as in the Double-blind Period for an additional 12 weeks.

Visits for PK must occur at least 24 hours after the last application of the IP to avoid contamination of the blood samples with any IP that may have remained in the skin after the last application.

Subjects should not apply IP on visit days until after the visit, unless they are participating in the PK substudy, in which case the IP will be applied in the clinic on Day 30 after the blood draw. Among subjects participating in the PK substudy, ensure the PK line is inserted before study drug application to prevent contamination with the IP and to protect the skin around the needle insertion point from study drug application.

9.3. Selection of Timing of Dose for Each Subject

Subjects will be randomized in a 1:1:1 ratio to trifarotene cream HE1 100 µg/g or 200 µg/g or vehicle cream. After Day 1, on which the study staff will apply the first administration of IP in the clinic, each subject will apply approximately the same amount of IP on up to 90% of their BSA twice weekly. It is suggested that each subject choose 2 specific days per week at least 3 days apart on which to apply their IP (e.g., Tuesday and Friday), and maintain that regimen throughout the study. Visits for PK must occur at least 24 hours after the last application of the IP to avoid contamination of the blood samples with any IP that may have remained on the skin after the last application. Subjects should not apply the IP on visit days until after the visit, unless they participate in the PK substudy, in which case the IP will be applied in the clinic on Day 30 after the PK blood draw.

All subjects will be provided with diaries in which to record study drug application (days/times) and any areas of skin not treated (e.g., due to local reactions).

If a subject misses an IP application, they should apply the IP as soon as they remember and record the date/time in the subject diary, then wait at least 3 days and continue their regimen.

Subjects should not shower, bathe, or swim for at least 4 hours after IP application. No occlusive dressings should be used on areas to which IP is applied.

Subjects who continue into the Open-label Extension will receive trifarotene cream HE1 200 µg/g and apply the same fixed dose in the same manner as in the Double-blind Period for an additional 12 weeks.

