- l. Samples for PK will be drawn from all subjects at Baseline and at each clinic visit. At selected sites among subjects who consent to participate in the PK substudy, samples will be taken predose and at 1, 2, 4, 8, 12, and 24 hours postdose on Day 1. On Day 30, IP will be applied in the clinic for PK substudy subjects, and PK samples will be taken predose and at 1, 2, 4, 8, 12, and 24 hours postdose. Trough levels will be drawn when the subjects are in the clinic for other study visits (i.e., Day 14, Day 60, and Day 90). Visits for PK must occur at least 24 hours after the last application of the IP to avoid contamination of the blood samples with any IP that may have remained in the skin after the last application.
- m. Study staff will apply initial dose of study drug in the clinic after Baseline measurements, and the amount of study drug used will be measured (i.e., 36-g tube will be measured before and after application to determine amount used) to determine fixed dose.
- n. Study drug provided in 50-g tubes (maximum single application is 36 g). Measure study drug tubes before dispensing; subjects must record days/times of study drug application in the diaries and any areas of skin not treated, e.g., due to local reactions). Dispense enough additional study drug until next visit (except at Day 90, unless subject consents to continue into OLE).
- o. Confirm study drug compliance by measuring tube weight and reviewing diary.

Table 2-2: Schedule of Events for Open-label Extension

	Open-label Treatment Period						Follow-up
	Telephone Visit (Day 97) ^a	Day 104 ± 5 days	Day 120 ± 7 days	Telephone Visit (Day 134)	Day 150 ± 7 days	Day 180 ± 7 days/ET	Day 194 or 14 days after End of Open-label Treatment
Visit		7	8		9	10	11
Week		14	16		20	24	26
Informed consent ^a							
Physical examination ^b						X	X
Vital signs (blood pressure and pulse)			X	X		X	X
Weight	X						
Record IGA ^c		X	X		X	X	X
VIIS ^d assessment		X	X		X	X	X
Roughness assessment ^c		X	X		X	X	X
Palm/sole assessment		X	X		X	X	X
Palm/sole fissuring assessment		X	X		X	X	X
Ectropion score			X	X		X	X
Clinical laboratory tests (hematology, chemistry, urinalysis) ^f			X			X	
Pregnancy test for female subjects (urine)			X		X	X	X
ECG			X			X	
PK blood sample collection ^g			X			X	
Application instructions, advice on emollient and sunscreen use ^h	X	X	X	X			

	Open-label Treatment Period						Follow-up

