10.2.2.1 Baseline Visit (Visit 2, Day 1)

The following procedures will be performed on Day 1 in the study clinic:

1. Review inclusion/exclusion criteria.
2. Record responses to DLQI and EQ-5D Quality of Life Questionnaires

3. Perform physical examination.
4. Record vital signs (blood pressure and pulse).
5. Record concomitant medications and concomitant therapies.
6. Record IGA.
7. Record VIIS.
8. Record roughness assessment.
9. Record palm/sole assessment.
10. Record palm/sole assessment of fissuring.
11. Record ectropion score.
12. At sites where the photographic substudy is conducted, take photographs of subjects who have provided informed consent for the photography.
13. Perform a 12-lead ECG.
14. Perform urine pregnancy test for WOCBP.
15. Collect blood and urine for routine laboratory tests (subject must be fasting; i.e., at least 8 hours).
16. Randomize via IWRS.
17. Collect a predose PK blood sample (all subjects).
18. Among subjects who consent to participate in the PK substudy, ensure that PK lines are placed before IP application. The IP will be applied in the clinic at this visit, and samples for PK will be taken at 1, 2, 4, 8, 12, and 24 hours postdose on Day 1.
19. Among subjects in the PK study, perform additional ECGs at times of serial sampling.
20. Clinic staff instructs subject on study drug application, applies initial study drug dose and measures amount used (i.e., study staff will weigh the 50-g tube before and after the first application to determine the fixed dose amount for each subject). If the product will be applied at home by someone other than the study subject, it is recommended that this person assist with application at this visit to learn how the IP is applied.
21. Assess and record local tolerance/AEs.
22. Dispense study drug and diaries.
23. Advise subjects regarding permitted emollient(s) for use on nontreatment days; use of emollient(s) and/or sunscreen on study drug treatment days within 4 hours before or after study drug application is prohibited. Remind subjects that at least 24 hours must have elapsed since IP application before their next visit. Subjects should not to apply IP on visit days until after the visit.

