10.2.2.3 Visit 3 (Day 14 ±5 days)

The following procedures will be performed on Day 14 in the study clinic:

1. Record responses to DLQI and EQ-5D Quality of Life Questionnaires.
2. Record concomitant medications and concomitant therapies.
3. Record vital signs (blood pressure and pulse).
4. Record IGA.
5. Record VIISIGA.
6. Record roughness assessment.
7. Record palm/sole assessment.
8. Record palm/sole assessment of fissuring
9. Record ectropion score.
10. Assess local tolerance.
11. Record AEs and review diary.
12. Collect a PK blood sample (all subjects).
13. Collect returned study drug tubes; confirm study drug compliance by weighing returned tube contents and reviewing diaries.
14. Instruct subject on study drug application, and advise subjects regarding permitted emollient(s) and/or sunscreen for use on nontreatment days; use of emollient(s) on study drug treatment days within 4 hours before or after study drug application is prohibited. Remind subjects that 24 hours must have elapsed since IP application before the subject's next visit. Subjects should not apply IP on visit days until after the visit.
15. Weigh new study drug tubes and dispense enough additional study drug until next visit, and new diary.

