10.2.2.4 Visit 4 (Day 30 ±7 days)

The following procedures will be performed on Day 30 in the study clinic:

1. Record responses to DLQI and EQ-5D Quality of Life Questionnaires.

2. Record concomitant medications and concomitant therapies.
3. Record vital signs (blood pressure and pulse).
4. Record IGA.
5. Record VIIS.
6. Record roughness assessment.
7. Record palm/sole assessment.
8. Record palm/sole assessment of fissuring
9. Record ectropion score.
10. At sites where the optional photographic substudy is conducted, take photographs of subjects who have provided informed consent for the substudy.
11. Assess local tolerance.
12. Record AEs and review diary.
16. Perform a 12-lead ECG
17. Perform a urine pregnancy test for WOCBP.
18. Collect blood and urine for routine laboratory tests (subject must be fasting at least 8 hours).
19. Collect a PK blood sample (all subjects).
20. Among subjects who consent to participate in the PK substudy, ensure that PK lines are placed before IP application. The IP will be applied in the clinic at this visit, and samples will be taken predose and at 1, 2, 4, 8, 12, and 24 hours postdose.
21. Among subjects in the PK study, perform an additional ECGs at times of serial sampling.
22. Collect returned study drug tubes; confirm study drug compliance by weighing returned tube contents and reviewing diaries.
23. Instruct subject on study drug application, and advise subjects regarding permitted emollient(s) and/or sunscreen for use on nontreatment days; use of emollient(s) on study drug treatment days within 4 hours before and after study drug application is prohibited. Remind subjects that 24 hours must have elapsed since IP application before the subject's next visit. Subjects should not apply IP on visit days until after the visit.
24. Weigh new study drug tubes and dispense enough additional study drug until next visit, and new diary.
25. Provide information about OLE option to study subject.

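### The Day 30 PK-substudy clinic dose is bound only by a 24-hour gap, so a compliant subject can be dosed on consecutive days and give a repeat-dose profile that does not reflect twice-weekly use

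*Protocol*

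**What the plan says.** The references are to the Amendment 2 text of the protocol.

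- **Interval before a PK visit.** Section 9.3: "Visits for PK must occur at least 24 hours after the last application of the IP". The stated reason is contamination of blood samples by product left on the skin.
- **Home regimen.** Application is twice weekly. On spacing, Section 9.3 says: "It is suggested that each subject choose 2 specific days per week at least 3 days apart". A 3-day wait is also given there, but only after a missed application.
- **Day 30 clinic dose.** Section 9.3 bars application on visit days until after the visit, except for those who participate "in the PK substudy, in which case the IP will be applied in the clinic on Day 30 after the PK blood draw". Section 9.2 makes the same exception for substudy subjects, "in which case the IP will be applied in the clinic on Day 30 after the blood draw". Table 2-1, footnote l: "On Day 30, IP will be applied in the clinic for PK substudy subjects, and PK samples will be taken predose". Section 10.2.2.4 repeats the order for Visit 4, with a ±7-day window.
- **Instruction beforehand.** Besides general application advice and the rule against applying before a visit on the same day, Section 10.2.2.3 (Visit 3) adds only this on timing: "Remind subjects that 24 hours must have elapsed since IP application before the" next visit.
- **Serial sampling.** There are two serial days. On the first, "samples for PK will be taken at 1, 2, 4, 8, 12, and 24 hours postdose on Day 1" (Section 10.2.2.1); the second is Day 30. Other visits yield troughs.
- **Objective.** Section 6.2 aims at systemic exposure under twice-weekly application on up to 90% of body surface.

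None of these places says that the Day 30 substudy visit must fall on a planned application day, or that the preceding home dose is to be moved.

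**The concern.** The 24-hour rule protects the blood sample, not the dosing interval. A site and a subject can follow every instruction and still place two full applications one day apart, immediately before and at the start of the only profile from which repeat-dose Cmax and AUC are obtained. That profile would carry residue from a dose given 24 hours earlier instead of 3 or 4 days earlier, and would overstate exposure under the intended regimen. Profiles with different preceding intervals would also be pooled, which adds variability in a substudy of at least 30 subjects.

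**Working it through.** The plan states no figure to reproduce. The check has two parts.

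**1. Calendar.** Inputs: first application on Day 1; twice weekly; two weekdays at least 3 days apart; visit window Day 30 ± 7, that is Days 23 to 37 (15 days).

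The Day 1 weekday recurs on Days 1 + 7k: Days 8, 15, 22 and 29. Nominal Day 30 is therefore the day after. To keep both weekly gaps at 3 days or more, the second weekday must be 3 or 4 days later:

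- Pattern Day 1/Day 4: planned days in the window are 25, 29, 32, 36. One day after a planned dose: 23, 26, 30, 33, 37 (5 of 15). Two days after: 24, 27, 31, 34 (4 of 15).
- Pattern Day 1/Day 5: planned days are 26, 29, 33, 36. One day after: 23, 27, 30, 34, 37 (5 of 15). Two days after: 24, 28, 31, 35 (4 of 15).

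These counts ignore clock time. The 24-hour rule is met one day after a dose only if that dose was no later in the day than the visit.

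The Day 1 weekday need not be kept. Seven weekday pairs satisfy the 3-day suggestion. Nominal Day 30 is one day after a planned dose in 2 of them, a planned day in 2, and two or three days after a planned dose in 3.

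**2. Size.** The protocol gives no half-life, so T is assumed, over a range. With mono-exponential decline and superposition of doses, AUC over 24 h relative to one isolated dose is

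1 + Σ 2^(−h/T), summed over earlier doses given h hours before.

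Example, T = 24 h, pattern 1/4:

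- Planned Day 29 (earlier doses 4, 7, 11, … days before): 1 + 2^(−4) + 2^(−7) + 2^(−11) + … = 1.071.
- Day 30 after a Day 29 dose (earlier doses 1, 5, 8, … days before): 1 + 2^(−1) + 2^(−5) + 2^(−8) + … = 1.535.
- Rise: 1.535/1.071 − 1 = about 43%.

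| Assumed T | Day 29, pattern 1/4 | Day 30, pattern 1/4 | Rise, 1/4 | Rise, 1/5 |
|---|---|---|---|---|
| 4 h | 1.000 | 1.016 | 1.6% | 1.6% |
| 8 h | 1.000 | 1.125 | 12.5% | 12.3% |
| 12 h | 1.004 | 1.251 | 24.6% | 23.5% |
| 24 h | 1.071 | 1.535 | 43.4% | 38.2% |
| 48 h | 1.371 | 1.970 | 43.6% | 38.1% |

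The Day 30 column uses exactly 24 h, the shortest gap allowed; a longer gap gives a smaller rise.

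**The case against.** The strongest points on the other side are these.

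- **The text may be read as already covering it.** The Day 30 dose is an exception to the rule on visit-day application, so it replaces a dose that would otherwise follow the visit. That is a fair reading, but it settles only the same-day home dose. It says nothing about a dose on the previous day.
- **The conditions are narrow.** The subject must keep the Day 1 weekday (or the visit must otherwise fall one day after a dose) and must have applied early enough in the day. A fasting visit followed by 12 hours of sampling probably starts in the morning, so an evening home dose on Day 29 would breach the 24-hour rule. This stands. The 5 of 15 days is not an estimate of how often the problem occurs.
- **The window allows a site to avoid it.** True; what is missing is the instruction to do so.
- **Day 1 gives a serial profile too.** If T is 24 h or less, the planned Day 29 AUC exceeds a single dose by at most about 7% in pattern 1/4, and by 1 + 2^(−3) + 2^(−7) + 2^(−10) + … = 1.134, about 13%, in pattern 1/5. Day 1 is then a useful substitute, provided absorption does not change under treatment. At T = 48 h, pattern 1/4 already gives 1.371, and the substitute is poor.
- **Affected profiles can be handled.** The diary records application times, actual sample times are recorded, and a predose sample is drawn. Profiles can be flagged, excluded, or partly adjusted where the terminal rate can be estimated. This stands.

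A reader might infer that the repeat-dose data are lost, or that safety is put at risk. The documents support neither. The shift is upward, hence conservative for safety, and adjustment is partly possible. Section 5.2 links irritation to daily use in healthy volunteers, not to one pair of consecutive days.

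**Conclusion.** The point holds as a minor gap in dosing instructions. Dosing on consecutive days at the Day 30 substudy visit is compliant under the Amendment 2 text, and the resulting Cmax and AUC would not describe twice-weekly use. For an affected subject the rise in AUC over 24 hours is about 2% to 44%, assuming mono-exponential decline, constant absorption and a half-life of 4 to 48 h; at the short end it is negligible. How many subjects would be affected cannot be determined. The substudy is optional and serves a secondary objective; the primary efficacy analysis is untouched. What analysis cannot supply is a replacement, because no later serial day is planned.

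It would be too much to say that the current protocol lacks this instruction. The document also holds statistics sections and a COVID-19 appendix from another, apparently later version, whose Sections 9 and 10 are not shown.

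**What to change.** In Sections 9.2, 9.3 and 10.2.2.4 and in Table 2-1 footnote l, require that the Day 30 substudy visit be scheduled, within the existing ±7-day window, on one of the subject's planned application days and at least 3 days after the last application. State that the clinic dose replaces that day's home dose. Give substudy subjects this instruction at Visit 3 together with the 24-hour reminder.

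Keeping the Day 1 weekday may be suggested, not required. Days 29 and 36 then qualify, each 3 or 4 days after the previous planned dose. If visits are assumed to run Monday to Thursday, so that the 24-hour draw falls on a weekday, each of the seven weekday pairs has at least one usable weekday. Every weekday occurs at least twice in 15 days, so each pair has at least two qualifying dates.

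The cost is a few sentences of protocol text, one scheduling instruction and slightly less visit flexibility. No new data item, sample or wider window is needed.
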